### **6.2.3. Sensitivity Analyses of Primary Efficacy Endpoint**

Sensitivity analyses will be performed to evaluate the robustness of the primary analysis results. Analyses will be performed for the overall population based on the outcome of the primary analyses including all subjects in the mITT set.

#### **6.2.3.1. Missing Data Analyses Based on Multiple Imputation**

The following sensitivity analysis based on multiple imputation will be performed, as appropriate, using the same statistical approach as the one used in the primary analysis:

- Subjects with treatment discontinuation or study withdrawal assessed as potentially related to study drug or lack of efficacy will have missing data after the discontinuation or withdrawal imputed via a control-based imputation based on the sham control subjects. This will be based on the mITT set.
  - Subjects who discontinue the treatment or study due to reasons that are potentially related to study drug or lack of efficacy include
    - Subjects who discontinue due to ocular adverse event, adverse event related to treatment, or adverse event related to injection procedure
    - Subjects who withdraw consent due to lack of efficacy (specify field includes ‘Lack of efficacy’) or not otherwise specified as not related to efficacy (specify field includes “Not specified”)
- Subjects with a monotone missing data pattern due to treatment discontinuation or study withdrawal will have missing data after the last assessment explicitly imputed by multiple imputation using a tipping point analysis method assuming missing not at random (MNAR). This will be based on the mITT set.

Imputation for the non-monotone missing pattern (i.e., arbitrary missing pattern) will be performed prior to the multiple imputation for the monotone missing pattern (i.e., where a missing GA area measurement at a visit for a subject implies that GA area measurements at all subsequent visits for that subject are missing).

For the nonmonotone missing pattern, missing value(s) between two visits with measured GA area will be imputed using the monotone data MCMC method, which was first proposed by Li (1988) and Liu (1993) described the algorithm. Multiple imputation will then be carried out for monotone missing pattern.

The two imputation methods will be implemented in SAS using the three standard steps to generate inference from imputed data: imputation step, analysis step, and pooling step. Details are illustrated with SAS codes in Section 1.2.2.

- The missing data are filled in 1000 times to generate 1000 complete datasets.
- The 1000 complete datasets are analyzed by using the same approach as for the analysis for the primary objective.
- The results from the 1000 complete datasets are combined for the inference.

Methods used in the imputation step are described below.

- Pattern Mixture Model Method (a copy-reference approach): The pattern mixture model method will be implemented.
  - Subjects with monotone missing data in the pooled sham arm will have missing data imputed based on the observed values in the pooled sham arm.
  - For the active treatment arms, subjects with monotone missing data who discontinued treatment or withdrew from the study due to reasons that are potentially related to study drug or lack of efficacy will have missing data imputed based on the pooled sham arm.
  - For the active treatment arms, subjects with monotone missing data who did not discontinue treatment or withdraw from the study due to reasons that are potentially related to study drug or lack of efficacy will have missing data imputed based on the observed values in the corresponding treatment arm.
- Tipping Point Analysis Method (a delta-adjusted approach): The tipping point analysis method will be implemented for each active treatment arm under the MNAR assumption by searching for a tipping point that reverses the conclusion regarding positive treatment effect. For the pooled sham arm, subjects will have missing data imputed based on the observed values in the pooled sham arm. For the active treatments, subjects with monotone missing data without treatment discontinuation or early withdrawal will have missing data imputed based on the observed values in the corresponding treatment arm. For the active treatment arms, subjects with monotone missing data due to treatment discontinuation or early withdrawal will have the missing data imputed based on the available values (observed values plus values imputed for non-monotone missing data) in the same treatment arm with a shift parameter added to the imputed values. Multiple imputation will be implemented on the differences between two consecutive visits, with the shift parameter allocated to the missing data point(s) proportionally across timepoints. (e.g. For a shift parameter of  $0.48 \text{ mm}^2$  at Month 12, incremental shifts of  $0.08 \text{ mm}^2$ , would apply to Month 2, Month 4, ... and Month 12, respectively.  $0.08 \text{ mm}^2 \times 6 \text{ visits} = 0.48 \text{ mm}^2$ ) The range of the shift parameters will be from  $0.06 \text{ mm}^2$  to  $0.72 \text{ mm}^2$  by increments of  $0.06$

mm^2 for Month 12 and 0.12 mm^2 to 1.44 mm^2 for Month 24 for the difference in the change of GA area from baseline between each pegcetacoplan arm (PM or PEOM) and Sham arm. The precision of the tipping point will be at two decimal points. A tipping point may not exist within reasonable clinical assumptions.

For each analysis, the number and percent of subjects without monotone missing data, the number of subjects with monotone missing data and a breakdown of reasons will be reported. The reasons will include monotone missing without treatment discontinuation or early withdrawal, monotone missing due to treatment discontinuation or early withdrawal due to reasons that are potentially related to study drug or lack of efficacy, and monotone missing due to treatment discontinuation or early withdrawal not due to reasons that are potentially related to study drug or lack of efficacy.

#### **6.2.3.2. Other Sensitivity Analyses**

The primary endpoint will also be analyzed without pooling the two sham arms (SM and SEOM). The comparison for pegcetacoplan and sham injection within each dose schedule (i.e., PM vs SM and PEOM vs SEOM, respectively) will be conducted using the MMRM analyses described in Section 6.2.2.

The primary endpoint will also be summarized excluding GA total area assessments with an indeterminate boundary. The summary and presentation of the observed values for the total area of GA lesion(s) by treatment group and visit described in Section 6.2.2 will be repeated. The summary and presentation of the analysis results for all timepoints described in Section 6.2.2 will be repeated.

#### **6.2.4. Supplemental Analyses of the Primary Efficacy Endpoint**

##### **6.2.4.1. COVID-19 Adjusted Estimand**

Despite the occurrence of the COVID-19 pandemic, the scientific question of interest in this study remains unchanged. The primary scientific research question of this study is to assess the effect of pegcetacoplan compared with that of sham at Month 12 on GA lesion progression under-real life conditions without COVID-19 pandemic impact.

To manage the increase in missed/not received injections due to COVID-19 pandemic (as collected on the eCRF), i.e., undertreatment with an expected relevant impact on efficacy, the hypothetical strategy will be used whereby assessments after the intercurrent event (relevant undertreatment) occurs will be set to missing/censored in the analysis. The threshold for missed/not received injections due to the COVID-19 pandemic is missing a pre-specified number of scheduled injections prior to the analysis timepoint of interest. For the Monthly schedule group, this is missing 2 or more injections and for the EOM schedule group, this is missing 1 or more injections prior to the Month 12 visit attributable due to the COVID-19 pandemic.

In terms of the underlying cause of the excessive missing/not received injections and subsequent missing data, it is assumed that the missingness resulting from censoring occurs at random because of the ongoing pandemic and not because of the subjects' unobserved outcome, so missing data resulting from this intercurrent event in the primary analysis model will be handled implicitly in the MMRM analysis.

The number of subjects with any censoring included in the model, the number of subjects with any censoring not included in the model, and the number of assessments censored by visit will be presented for each treatment group.

All summaries and presentations of the observed values for the total area of GA lesion(s) in the study eye by treatment group and visit described in Section 6.2.2 will be repeated for the COVID-19 adjusted estimand. All summaries and presentations of the analysis results for all timepoints described in Section 6.2.2 will be repeated for the COVID-19 adjusted estimand. The same plots as for the primary endpoint analysis will be presented.

In addition, a supplemental analysis will also be performed where the threshold for missed/not received injections will be restricted to external events attributable to COVID-19. These events are defined based on the COVID-19 collection form and include COVID-19 diagnosis, COVID-19 Suspected, Site Closure, Travel Ban, Shelter in Place, City Lockdown, and Other. Except for the plots, the analyses described above will be repeated for the threshold based only on these external events attributable to COVID-19.

#### **6.2.4.2. Per Protocol Set**

The main analysis described in Section 6.2.2 will be repeated using the Month 12 PP set to investigate the impact of changing the population in the estimand. Any GA lesion area assessments that are deemed not valid according to what is described in Section 4.5 will be set to missing in this analysis. The summary and presentation of the observed values for the total area of GA lesion(s) by treatment group and visit described in Section 6.2.2 will be repeated. The summary and presentation of the analysis results for all timepoints described in Section 6.2.2 will be repeated.

#### **6.2.4.3. Rate of Change Analyses**

The mean rate of change in GA area (i.e., slope) will be compared between each pegcetacoplan arm and the pooled sham arm by use of linear mixed effects model assuming time as continuous and linear (“slope model”). The analysis model will include treatment (PM, PEOM, sham), presence of choroidal neovascularization in the fellow eye at baseline (Yes, No), baseline GA lesion area ( $< 7.5 \text{ mm}^2$  or  $\geq 7.5 \text{ mm}^2$ ) as fixed effects, time (study month, continuous assuming linearity), the time  $\times$  treatment interaction term as well as the baseline GA lesion area  $\times$  time interaction term. The response variable will be the GA lesion area. A common unstructured covariance matrix will be used to model the within-subject errors, the sandwich estimator will be used to estimate the standard errors of the fixed effects parameters, and the degrees of freedom will be partitioned into between-subject and within-subject portions. If there are convergence problems with the model, then a heterogeneous autoregressive (1) covariance matrix will be used. If convergence problems still exist, an autoregressive (1) covariance matrix will be used. The mean rate of change (slope), standard error, and confidence interval will be estimated for the baseline to Month 12 as well as the baseline to Month 6 and Month 6 to Month 12 periods for each treatment group. In addition, the estimated difference in slopes among the treatment groups along with the 95% CIs and p-value will be reported. The slopes and 95% CIs will be converted to an annualized rate of growth for each period and each treatment group.

The observed values for the total area of GA lesion(s) will be summarized by treatment group and visit for the baseline to Month 6 and Month 6 to Month 12 time periods. Summaries will present the descriptive statistics for baseline, absolute values and change from baseline to

Month 6 and change from Month 6 to Month 12 data. In addition, the annualized rate of growth for each time period will also be presented.

The mean rate of change in GA area will be compared between each pegcetacoplan arm and the pooled sham arm by use of a piecewise linear mixed effect model assuming time as continuous and piecewise linear (“piecewise slope model”). The analysis to be performed will be similar to what is described above in the “slope model” except that a knot at the Month 6 visit will be added which allows for the slope of lesion growth to differ between the two periods for each of the treatment groups. The same presentation as for the “slope model” will be prepared except for the Baseline to Month 12 slope. Additionally, an investigation of the impact of changing the knot to Month 2, 4, 8, 10 will be explored if necessary.

### **6.2.5. Subgroup Analyses of Primary Efficacy Endpoint**

Subgroup analyses will be performed to evaluate the consistency of the primary analysis results across subgroups defined by demographic and baseline characteristics. Analyses will be performed for the primary efficacy endpoint (change from baseline in total area of GA lesion(s) in the study eye at Month 12) for each of the following subgroups (as appropriate per actual subgroup sample size, levels with low sample size may be pooled to allow for an analysis to be conducted):

- Age Group (<75 years, 75 to <85 years, ≥85 years)
- Sex (male, female)
- Race (White, Black or African American, Asian, American Indian or Alaskan Native, Native Hawaiian or other Pacific Islander, multiple, unknown)
  - Note: If most subjects (e.g., >90%) are of a single race, this analysis will not be conducted.
- Geographic Region (United States vs Rest of World)
- Subgroups indicative of disease severity at baseline
  - Study eye baseline GA lesion size (<7.5 mm^2; ≥7.5 mm^2)
  - Study eye baseline GA lesion size categories (approximately tertiles based on APL2-303/304 combined data\*)
  - Study eye baseline NL-BCVA categories (≥70, ≥60 - <70, ≥35 - <60, <35 ETDRS letters)
  - Study eye baseline NL-BCVA categories (<60 vs. ≥60 ETDRS letters)
  - Study eye baseline LL-BCVA categories (approximately tertiles based on APL2-303/304 combined data\*)
  - Study eye baseline monocular maximum reading speed categories (approximately tertiles based on APL2-303/304 combined data\*)
  - Baseline FRI Level (1,2,3,4)
  - Study eye mean threshold sensitivity of all points categories (approximately tertiles)
- Subgroups associated with GA progression
  - Study eye baseline GA focality (multifocal, unifocal)

- Study eye baseline GA lesion location (subfoveal involvement, without subfoveal involvement)
- Baseline GA laterality (bilateral GA (with or without CNV in fellow eye) vs. Study eye GA Only)
- Baseline CNV in fellow eye (Fellow eye CNV vs. No fellow eye CNV)
- Study eye baseline LLD categories (<20 vs.  $\geq$  20 ETDRS letters)
- Study eye baseline LLD categories (approximately tertiles based on the APL2-303/304 combined data\*)
- Study eye baseline NL-BCVA (<60 vs.  $\geq$ 60 ETDRS letters) and LLD (<20 vs.  $\geq$  20 ETDRS letters) combinations

\*Approximately tertiles will be specified consistently across the APL2-303/304 studies to the nearest clinically relevant level.

For the primary efficacy endpoint, the approach described in the Section 6.2.2 will be used for each subgroup analysis based on the data subset for the subject subgroup of interest. Baseline covariates included in the main analysis but no longer relevant given the subgroup of interest will be excluded from the model. The estimated treatment effects (PM vs. Sham; PEOM vs. Sham) and corresponding 95% CIs and p-values from the models will be displayed graphically for each pegcetacoplan treatment arm and each level of the subgroups specified (e.g., via forest plots).

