### 6.2.2. Main Analysis of Primary Efficacy Endpoint

The primary endpoint will be analyzed in the mITT population with subjects grouped according to the treatment assigned at randomization.

A MMRM model will be used to analyze the primary endpoint. The analysis model will include treatment (PM, PEOM, sham), presence of choroidal neovascularization in the fellow eye at baseline (Yes, No) and baseline GA lesion area ( $< 7.5 \text{ mm}^2$  or  $\geq 7.5 \text{ mm}^2$ ) as fixed effects, time (study month, categorical) as a factor, the time  $\times$  treatment interaction term, and the baseline GA lesion area ( $< 7.5 \text{ mm}^2$  or  $\geq 7.5 \text{ mm}^2$ )  $\times$  time interaction term. The least square [LS] mean change from baseline to Month 12 will be estimated from the model for each of three arms as well as the comparisons of each of the three arms to each other. For other time points of interest, LS mean change from baseline will be estimated and compared between treatments. For each estimated LS mean, the corresponding 95% CI will be presented based on the model. For the comparison of the LS means, the corresponding 95% CI and the 2-sided P-value along with the percentage difference (difference in LS means between the arms/the comparison group LS mean) will be

presented. A common unstructured covariance matrix will be used to model the within-subject errors, the sandwich estimator (Diggle, Liang, and Zeger 1994) will be used to estimate the standard errors of the fixed effects parameters, and the degrees of freedom will be partitioned into between-subject and within-subject portions. If there are convergence problems with the model, then a heterogeneous autoregressive (1) covariance matrix will be used. If convergence problems still exist, an autoregressive (1) covariance matrix will be used. The LS mean of the change from baseline in the total area of GA lesion(s)  $\pm$  the standard error will be plotted over time by treatment group.

The observed values for the total area of GA lesion(s) will be summarized by treatment group and visit for both the study and the fellow eye. Summaries will present the descriptive statistics for baseline, absolute values and change from baseline data by visit.

The mean change from baseline in the total area of GA lesion (s) in the study eye  $\pm$  the standard error will be plotted over time by treatment group.

All GA lesion (s) size data will be listed for the ITT set.

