#### **6.3.3. Sensitivity Analyses of Key Secondary Efficacy Endpoints**

The missing data analyses based on imputation described in Section 6.2.3.1 will be repeated for the key secondary efficacy endpoints at the time of the final study analysis for the full 24 months only. The key secondary endpoints will also be analyzed without pooling the two sham arms (SM and SEOM) for the full 24 months only.

In addition, to assess the potential effect of different assessment tools, the main analysis of monocular maximum reading speed will be repeated by reading chart type.

---

 approximated from 6/18; see <https://icd.who.int/browse11/l-m/en#/http://id.who.int/icd/entity/1103667651>

Maximum reading speed with adjustment for reading inaccuracy will also be analyzed, only in the study eye, for the first 12 months as well as the full 24 months.

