##### NL-BCVA

- Study eye fixation stability (95% BCEA) categories (approximately tertiles)

For each endpoint, a MMRM similar to that specified for the main analysis of the key secondary endpoints (Section 6.3.2) will be used for each subgroup analysis based on the data subset for the subject subgroup of interest. Baseline covariates included in the main analysis but no longer relevant given the subgroup of interest will be excluded from the model. The estimated treatment effects (PM vs. Sham or PEOM vs. Sham) and corresponding 95% CIs and p-values from the models will be displayed graphically for each pegcetacoplan arm and each level of the subgroups specified (e.g. via forest plots).

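### The subgroup analyses aim at consistency of effect, but no between-level difference or treatment-by-subgroup interaction is planned, and the per-level p-values cannot stand in for it

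*SAP*

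**What the plan says.** SAP 6.2.5 states its purpose: "Subgroup analyses will be performed to evaluate the consistency of the primary analysis results across subgroups defined by demographic and baseline characteristics". As to method, the approach of SAP 6.2.2 "will be used for each subgroup analysis based on the data subset for the subject subgroup of interest", leaving out covariates that no longer apply. Each level of each factor therefore gets its own MMRM. What is reported is the PM and PEOM effect against sham in each level, and "corresponding 95% CIs and p-values from the models will be displayed graphically for each pegcetacoplan treatment arm and each level of the subgroups specified", with forest plots given as the example.

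The refitted model (SAP 6.2.2, with code in Appendix 1, section 1.2.1) contains treatment, fellow-eye CNV, baseline lesion category and visit. Its only interactions are visit × treatment and lesion category × visit. Neither the SAP nor the protocol contains a treatment × subgroup term, a between-level contrast, a heterogeneity test or a criterion for consistency.

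SAP 6.3.5 takes over the same subgroup list for the key secondary endpoints, adds a few factors, and plans the same display: "corresponding 95% CIs and p-values from the models will be displayed graphically for each pegcetacoplan arm and each level of the subgroups specified". It states no separate aim. SAP 6.2.6 repeats the scheme for the 24-month lesion data, and SAP 6.4.1 applies it to LL-BCVA.

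**The concern.** Consistency is a question about the difference in effect between levels, and its null hypothesis is that the effects are equal. The planned p-values test another null, that the effect within one level is zero. Whether such a p-value falls below 0.05 depends on how many subjects the level holds as well as on the effect.

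A plot with p<0.05 in one level and p>0.05 in another can be read as showing that the drug works only in some patients, even when the effect is the same in all. That reading would matter most for factors such as subfoveal involvement, laterality and fellow-eye CNV. PEOM is the more exposed arm because its whole-trial power is lower. Conversely, if the effect really does differ between levels, no planned line states by how much or how precisely.

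**Working it through.** **Inputs.** 200 subjects per group after pooling sham; mean growth 1.47 (PM), 1.70 (PEOM) and 2.13 (sham) mm²/year; SD 1.50 or 1.25 mm² (Protocol 12.5, SAP 3.4). The effects are 2.13 − 1.47 = 0.66 for PM and 2.13 − 1.70 = 0.43 for PEOM. Efficacy tests are two-sided (SAP 6). The documents give no level sizes, so equal sizes are assumed: 100, 66.7 or 50 per group for two, three or four levels. Race is left out because 6.2.5 allows it to be dropped. The remaining list has 18 factors: nine with two levels, six with three and three with four.

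**The plan's own power.** A one-way ANOVA contrast (noncentral t, 597 df) at alpha 0.0495 and SD 1.50 gives 99.2% for PM and 81.5% for PEOM. At SD 1.25 it gives 92.9% for PEOM. All three match SAP Table 1.

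**Power within one level, same true effect in every level.** SE = SD × √(2/n), and power p = Φ(effect/SE − 1.96). For PEOM with two levels at SD 1.50, SE = 1.50 × √(2/100) = 0.212, 0.43/0.212 = 2.03, and p = Φ(0.07) = 52.7%.

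**Mixed pattern.** The chance that a factor with k levels shows some significant and some non-significant levels is 1 − p^k − (1 − p)^k. For the same case it is 1 − 0.527² − 0.473² = 49.9%.

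| Arm | Levels | Per-level power, SD 1.25 / 1.50 | Mixed pattern, SD 1.25 / 1.50 |
|---|---|---|---|
| PM | 2 | 96.2% / 87.5% | 7.3% / 21.8% |
| PM | 3 | 86.2% / 71.9% | 35.7% / 60.6% |
| PM | 4 | 75.2% / 59.5% | 67.7% / 84.8% |
| PEOM | 2 | 68.2% / 52.7% | 43.4% / 49.9% |
| PEOM | 3 | 51.0% / 38.0% | 75.0% / 70.7% |
| PEOM | 4 | 40.5% / 29.9% | 84.8% / 75.1% |

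For PEOM with three or four levels the mixed share is lower at the larger SD only because all levels are then more often non-significant together.

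**Unequal levels.** A level holding 20% of subjects has power 66% / 50% for PM and 34% / 25% for PEOM (SD 1.25 / 1.50).

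**The test that matches the question.** A treatment × subgroup heterogeneity test with k − 1 df, simulated with 400,000 draws per case under a uniform effect, rejected in 4.9% to 5.1% for two, three and four levels, both arms and both SDs.

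**What that test can detect.** For a 50:50 factor the SE of the difference between two level-specific effects is √2 × SD × √(2/100), which is 0.25 (SD 1.25) or 0.30 (SD 1.50) mm². For 80% power the true difference must be (1.96 + 0.84) × SE, about 0.70 or 0.84 mm². With 18 factors and two comparisons there are 36 tests, and 36 × 0.05 = 1.8 chance findings are expected under uniform effects.

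**The case against.** A reader might infer that under this plan a uniform effect will look inconsistent. The documents do not support that as it stands. The forest plots also show estimates and 95% CIs, and the SAP nowhere says that consistency means p<0.05 in every level. The mixed patterns above mislead only a reader who sorts levels by significance. This part of the objection stands; the point is that the p-values do not answer the stated question, yet are displayed for it.

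Nor is the information lost. Levels of one factor are disjoint subjects fitted separately, so the difference between two estimates has SE √(SE₁² + SE₂²), recoverable from the planned CIs. This too stands, but the reader would have to do the calculation for each factor and arm, and the plan does not commit to it.

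The SAP also expects longitudinal modelling to raise power above its cross-sectional figures. At an SD of 1.0, assumed here to represent such a gain, the mixed pattern in two-level factors falls to 0.7% for PM but remains 24% for PEOM.

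A reader might extend the point to SAP 6.3.3, where, "to assess the potential effect of different assessment tools, the main analysis of monocular maximum reading speed will be repeated by reading chart type" (6.4.3 does likewise for critical print size). That extension does not hold. It is a sensitivity re-run with no stated subgroup-consistency aim. Protocol Appendix G ties the choice of chart to country and language, so a treatment × chart interaction would mix the tool with country.

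Finally, the remedy has its own weakness. For an even split at SD 1.50 the detectable difference of 0.84 mm² exceeds the whole PM effect of 0.66, and a non-significant interaction could be misread as proof of consistency. That stands, and it is why the interval should lead.

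**Conclusion.** The stated aim and the planned output do not match, and this should be corrected. SAP 6.2.5 asks about consistency, yet no between-level difference or interaction is estimated or tested; 6.3.5 carries the gap over.

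The size rests on equal-sized levels, a uniform effect at the planning values, and a cross-sectional comparison without covariates. The problem is mainly one for PEOM and for factors with three or four levels; for PM in balanced two-level factors it is modest. Unequal splits weaken the smaller level further. Several factors overlap (lesion size, NL-BCVA and LLD each appear more than once), so the 1.8 chance interactions are an expectation and not a count of independent events.

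The figures apply to lesion area only. SAP 3.4 says that power was not calculated for the key secondary functional endpoints, so for 6.3.5 the point is one of method, without a magnitude. Nor should a reader infer a threat to the trial's main conclusions: subgroups lie outside the testing sequences in SAP 6.2.1 and 6.3.1.

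**What to change.** In SAP 6.2.5 and 6.3.5, fit one model per subgroup factor on the full mITT set. Take the main-analysis model for the endpoint and add subgroup, subgroup × visit, treatment × subgroup and treatment × subgroup × visit, omitting any term already present (as for lesion category and fellow-eye CNV).

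At Month 12 for the primary endpoint and Month 24 for the key secondary endpoints, report separately for PM vs Sham and PEOM vs Sham:

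- the effect and 95% CI in each level;
- the between-level difference in effect with its 95% CI, against a named reference level where there are more than two, as the main output;
- one nominal interaction p-value per factor, labelled exploratory and unadjusted for multiplicity.

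Remove the within-level p-values from the forest plots, or label them as not for judging consistency. State that a non-significant interaction does not establish consistency.

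The cost is SAP wording and modest programming. No new data are needed, and alpha and the primary test do not change. A single model imposes a common covariance structure and common covariate effects across levels, which separate fits avoid. The limited power and the expected chance interactions remain, and should be stated beside the results.
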